The inconsistent radiographic technique and centring points have also been highlighted by patient exclusions in orthopaedic research studies because radiographs do not meet pre-determined positional and quality criteria. Interestingly, issues of radiographic technique were also identified in the 2014 NICE guidelines for hip OA³ which states that differing radiographic protocols contribute to a lack of robust evidence around their use. Radiography textbooks are also contradictory, resulting in local variation. Indeed one textbook suggests flexing a patients' hips and knees slightly to correct for pelvic tilt, a factor unlikely to be appreciated by clinicians, with potential to lead to misinterpretation.

Importantly, no previous study has considered the radiation dose implications of patient posture or defined the standardised positioning required to introduce this as a mainstream investigation. Patient position has potential to influence radiation dose through reduced soft-tissue compression and increased overlying abdominal tissues. This would have significant implications for image quality, which in turn could impact on clinical decision making. National dose reference levels (DRLs) do not exist for erect positioning, a non-standard technique, meaning that there is no parameters for dose in this projection, despite a small number of Trusts already adopting this technique. Interestingly, authors have demonstrated opportunities to reduce radiation dose with increased distance or orientation on digital equipment, but these were only undertaken supine using an anthropomorphic phantom^{24,25,26} and have not been translated into clinical practice. As a result this research hopes to develop a patient centred evidence base for the positioning and exposure factors for erect AP pelvis projections.

Key research questions

The key research questions requiring an answer are:

- 1. Does pelvic radiography performed in the erect position result in an increase in radiation dose to the patient?
- 2. Does pelvic radiography performed in the erect position demonstrate clinically significant changes in image quality when compared to a supine X-ray image?
- 3. Are erect pelvic radiographs acceptable to patients in their performance?
- 4. Would the change impact on service delivery, in terms of examination time?

Aims

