This study aims to ensure that X-ray images of the pelvis are performed using evidence based protocols. It will also determine if patient posture (erect or supine) has an effect on radiation dose, image quality and diagnostic measures.

[figure not shown]
The study objectives are to:

- Develop trial procedures, imaging protocols and patient information for a future study
- Estimate the recruitment rate for a prospective study which will the diagnostic and dose differences between supine and erect pelvic radiographs
- Identify the recruitment and refusal rates to such research.

Study site

A single NHS Trust is being used to control for variations in technique and equipment. Mid Yorkshire Hospitals NHS Trust (MYH) comprises 3 hospital sites, Dewsbury District Hospital, Pinderfields Hospital (Wakefield) and Pontefract Hospital. Almost 8000 adult patients were referred from either their GP or as an outpatient to the Trust radiology department for pelvis or hip radiographs in 2016, including those referred for a hip x-ray where a full pelvic radiograph is performed as standard. The age profile of these patients is demonstrated in Figure 1. This demonstrates that the median age of this patient population is 65, with 80% of all patients being over 50 years in age.

Method

Phase One: Patient modelling

The initial data collection will focus on ascertaining the patient population and how physical characteristics (body shape) differs between the erect and supine positions. This will be through standardised measures obtained in both positions.

Sample size

A cohort of 180 patients who are attending for radiography of the hip or pelvis from either an outpatient (OP) clinic or their general practitioner (GP) will be recruited. Specifically the study aims to achieve a minimum of 30 patients in each of the following categories:

Underweight/Normal (BMI<25)

Overweight (BMI 25-30)

Obese/Morbidly obese (BMI>30)

Inclusion criteria

All patients who attend for radiographs of the hip or pelvis from a MYH OP clinic or their GP will be eligible for inclusion to the study. It is estimated that there are approximately 60 eligible patients per week attending each hospital site within the study organisation.

Exclusion criteria

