The recruited participant will be asked to change into a gown appropriate to their radiological examination and then taken to a private room (x-ray room) to maintain dignity and privacy. They will then have various measures undertaken by the research team member (see instruction sheet appendix 3).

These will include:

- Height (m)
- Weight (kg)
- Body circumference
- Source-Object Distance (i.e. x-ray tube to patient skin, as a proxy for body diameter)

A small group of radiographers will be trained to undertake the specific study parameters to ensure consistent data collection (Appendix 4). They will then continue with the radiographic examination as requested by the referring clinician.

Data analysis

The data collected will allow modelling of the change in patient body shape between the two projections. Variations in shape between BMI subgroup, gender and age will be assessed. Mean and standard deviations will be calculated if the resultant data are approximately normally distributed and median (ISR) measures will be determined for non-parametric data.

[figure not shown]
Phase Two: Phantom Experiment

An anthropomorphic phantom of the abdomen and pelvis will be used to investigate the optimal image acquisition protocol based on the anatomical changes identified in phase one. No patients will be recruited for this part of the study.

The outcome of the phantom study will be specific kV and mAs settings or automatic exposure control (AEC) settings for the different techniques and comparison of the phantom dose data with national diagnostic reference levels.

Based on the variation in mean measures between the different position and body habitus in phase one a Kyoto phantom will be physically altered with the addition of appropriately positioned soft tissue density mimicking material. This will enable multiple exposures of the phantom to be made at different distances and exposure factors to ascertain whether automatic exposure devices can be reliably used in both of the patient positions or whether specific exposure charts should be calculated regarding a patient's body habitus.

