An example of the acquisition procedure is demonstrated in figure 2 below. The resultant images will be analysed for quality in relation to visualisation of the bony anatomy of the pelvis and hip joint. Based on a previously validated technique²⁶ radiation dose (entrance surface dose (ESD) and effective dose (ED)) will be calculated using a commercially available computer software system which utilises Monte Carlo code dose simulation (PCMXC). Calculations require the source-object distance, mAs and peak tube potential values (kV) to be entered for each data point.

Phase Three: Pelvic Radiograph Acquisition

This phase will compare radiographs obtained on the same patient in two different positions, supine and erect. The supine positioning is that which is currently undertaken within the imaging department. The erect positioning technique and acquisition parameters will be informed by the earlier phases of the research.

Sample size

A single arm pilot study is planned with no attempt at this time to undertake sub-group analysis. A minimum of sixty patients will be recruited to this study based on the premise of the future trial demonstrating a 5% difference in pelvic tilt between the 2 projections (95% confidence interval), ²⁷ this exceeds 10% of the potential future trial requirements ^{28,29} and includes a minimum of 12 participants per subgroup. ³⁰

The future trial is estimated to require a minimum sample of 474, based on the same calculations. To allow for the inability to perform the erect x-ray, exclusion based on image quality and to enable sub-group analysis, it is planned that the sample recruited would be 800. The subgroup analysis for referral reason will comprise:

- 1. Young adult with hip pain (18-40)
- 2. Patient with evidence of hip dysplasia
- 3. Older adult referred with symptoms or diagnosis of OA
- 4. Previous hip replacement under monitoring

Inclusion criteria

All patients who attend for general radiography of the hip or pelvis from their general practitioner or outpatient clinic will be eligible for inclusion to the study. It is estimated that there are approximately 60 eligible patients per week attending any one hospital site within the study organisation.

Exclusion criteria

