Each patient will be radiographed in two positions, supine with a SID of 115 cm (current technique employed within the imaging department) and erect with a SID of 180cm (new comparison technique). Additionally the patient will have their height and weight measured to confirm the appropriate exposure parameters established in phase two.

The supine and erect radiographic examinations will be performed in a random order with the preprinted data collection sheets indicating the order of the patient. This will be established using a random number generator. This procedure ensures that the patient preference cannot be related to the examination order.

Data collection and management

A data collection sheet will be used to record information about each study participant and the imaging parameters (Appendix 7). The data includes the anatomical measures (phase one and three) and exposure parameters (phase three only) and the patient will be asked their preference for the imaging technique (erect or supine). The data will be transcribed as soon as practicable into the Trust research management system EDGE with patient identifiable data being removed.

The additional erect pelvis projection will be stored on the MYT PACS system. Additionally anonymised copied will be stored to a study teaching file on PACS using their unique study identifier to allow blinded image review. The PI is a PACS administrator and will ensure this data is securely managed.

On completion of the recruitment data validation will take place to ensure there are no transcription errors and missing data. The final data set will be exported into Microsoft Excel for analysis. Further statistical analysis will take place using PCMXC and SPSS.

Data analysis

The phase three data will allow the comparison of the radiation dose (entrance surface dose (ESD) and effective dose (ED)) will be calculated using a commercially available computer software system which utilises Monte Carlo code dose simulation (PCMXC). Calculations will use the source-object distance, mAs and peak tube potential values (kV) for each exposure.

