The number of radiographers able to obtain study images will be limited to provide quality assurance with the erect technique which is non-standard. These will undergo training and images will be assessed for quality throughout the study, providing opportunity for interventions if any variation from the protocol is identified.

Additional radiation dose reduction techniques will be adopted and these will be optimised during phase two of the study. Monitoring of patient radiation dose will be paramount, as with any imaging

study. A dose constraint will be established prior to ethical approval in line with the Ionising Radiation (Medical Exposure) Regulations 2000 (IRMER), if it is identified that certain patient groups are approaching this constraint a decision will be made to limit recruitment.

Patients will be informed of the study in advance, either with their radiology appointment letter or with clinic information depending on referral route. In addition posters will be distributed to GP surgeries and OP clinics to raise awareness. Patients will be provided information leaflets and the opportunity to discuss the study prior to the consent process.

Participants will be consented to the measures (and additional x-ray – phase 3 only) and will be able to withdraw their consent at any time during the radiology appointment without detriment to their care. Patients will be consented at time of their x-ray but will be given the chance to withdraw their data up to the start of data analysis, which is expected to be up to one month from end of recruitment. This information will be provided to patients. Permission to perform the additional measures (and x-ray) will be obtained in private prior to the examination within the radiology department. Confidentiality of participants will be maintained and the processes for data management will be compliant with the Data Protection Act (1998).

Source data, consent forms and patient screening questionnaires will be stored in a locked filing cabinet within a locked research office. Data transfer will be by encrypted Trust devices. Only the research team will have access to this data. All reports and dissemination of findings will only include anonymised data.

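### In phase three, posture and source-image distance change together, so the dose and image-quality contrast compares two techniques and cannot be credited to posture

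*Protocol*

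**What the plan says.** **Acquisition.** The protocol (Phase Three, Study procedures) images every patient twice: "supine with a SID of 115 cm (current technique employed within the imaging department) and erect with a SID of 180cm (new comparison technique". The opening of Phase Three adds, for supine, "The supine positioning is that which is currently undertaken within the imaging department", and for erect, "The erect positioning technique and acquisition parameters will be informed by the earlier phases of the research". The Ethical Consideration section caps erect imaging at a single exposure per patient. The order of the two examinations is randomised, and image readers are blinded to technique.

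**Claims.** The Aims section says: "It will also determine if patient posture (erect or supine) has an effect on radiation dose, image quality and diagnostic measures". Research question 1 asks: "Does pelvic radiography performed in the erect position result in an increase in radiation dose to the patient". The Background reports phantom work, done supine, in which more distance offered a way to lower dose. It also says that standing may affect dose through less soft-tissue compression and more overlying abdominal tissue.

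**Phase two.** Its output is "specific kV and mAs settings or automatic exposure control (AEC) settings for the different techniques". In phase three each patient has "height and weight measured to confirm the appropriate exposure parameters established in phase two". The Ethical Consideration section adds: "Additional radiation dose reduction techniques will be adopted and these will be optimised during phase two of the study".

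**Data.** The phase-three Data analysis section bases the entrance and effective dose calculations on source-object distance together with the tube settings. The phase-three data sheet (Appendix 7) has fields for kV, mAs, DAP, EI, height and weight, but none for source-object distance.

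**The concern.** The aim promises an effect of posture, while the acquisition changes posture and distance at the same moment in every patient. The two could push dose in opposite directions: on the protocol's own account longer distance can lower it, and more tissue in the beam when standing would raise it. A result of no increase could therefore mean that standing costs nothing, or that a real cost was cancelled by distance. The Summary says the pilot is to lead to a grant application on whether posture affects image quality or dose, so the misreading would carry into the design of the larger study.

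**Working it through.** **1. Can the effects be separated?** Let E = 1 for erect and 0 for supine. The fixed distances give SID = 115 + 65E for every image. Suppose an outcome depends on the patient, on posture (β per switch to erect) and on distance (γ per cm). The within-patient difference then estimates β + 65γ. Only the sum is estimable. Randomised order removes order effects and blinding removes reader bias, but neither acts on this sum. The planned 60 patients, or the 474 named for the future trial, make it more precise without splitting it.

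**2. How large can the distance part be?** The protocol gives no figure to reproduce, so the geometry has to be assumed: trunk thickness T = 20-30 cm, gap g from skin to detector = 4-8 cm, and equal detector exposure in both images. Source-skin distance is SID − T − g. With posture held constant:

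entrance dose ratio (180 vs 115 cm) = [(180 / SSD at 180) / (115 / SSD at 115)]²

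| T, g (cm) | SSD at 115 | SSD at 180 | Ratio | Fall |
|---|---|---|---|---|
| 20, 4 | 91 | 156 | 0.834 | 17% |
| 25, 6 | 84 | 149 | 0.779 | 22% |
| 30, 8 | 77 | 142 | 0.720 | 28% |

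Wider assumptions (T 18-35 cm, g 5-10 cm) give ratios of 0.84 to 0.66, a fall of 16-34%.

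**3. Can this hide a posture penalty?** Assume 24 cm thickness, a 7 cm gap, and a soft-tissue half-value layer (HVL) of 3-4 cm. Let standing add x cm of tissue. The supine reference is (115/84)² = 1.874. Erect entrance dose relative to supine is then 2^(x/HVL) × (SID / SSD)² / 1.874.

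- x = 1, common SID of 115 cm: SSD = 83, (115/83)² = 1.920. The ratio is 1.22 (HVL 4) to 1.29 (HVL 3).
- x = 1, as designed at 180 cm: SSD = 148, (180/148)² = 1.479. The ratio is 0.94 to 0.99.
- x = 2: 1.48 to 1.67 at a common SID, and 1.13 to 1.27 as designed.

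Under these assumptions a posture penalty of about 25% would be observed as no increase, and a penalty of about 50-65% would be roughly halved or more.

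**4. Effective dose.** The effect weakens with depth. With T = 25 and g = 6, tissue 10 cm below the skin lies 94 cm from the source at SID 115 and 159 cm at SID 180. The ratio is [(180/159) / (115/94)]² = 0.86, a fall of 14% against 22% at the skin.

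**5. Linear measurements.** Magnification is SID / (SID − d), with d the distance of the structure from the detector (assumed). The ratio of 180 to 115 cm is 0.967 at d = 10, 0.949 at d = 15 and 0.937 at d = 18. Lengths would appear about 3-6% shorter on the erect image with no change in anatomy.

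**The case against.** The best defence is that phase three was meant as a comparison of techniques. The protocol labels the two acquisitions as current and new technique, and research question 1 stands beside questions on acceptability and examination time, so it can be read as asking about the service as delivered. The listed objectives concern procedures and recruitment for a later study. The limit of one erect exposure is a deliberate ethical choice, so separating the effects within patients was never available. Phase one measures body shape in both postures at a common 115 cm, and phase two exposes an adapted phantom at several distances.

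Most of this stands. The package comparison is legitimate and answerable. It does not rescue the sentence in the Aims, which names posture as the cause, and the visible text states no step that uses phases one and two to isolate the distance effect in phase three.

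A reader might also infer several stronger points that the documents do not support:

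- **That only the erect technique is optimised, so optimisation is fully confounded with posture too.** Phase two yields settings for more than one technique, and phase three does not restrict the phase-two parameters or the dose-reduction measures to erect. The retained current practice refers to supine positioning. The scope is unclear.
- **That the magnification shift matches the 5% difference behind the sample size.** That figure concerns pelvic tilt, which the Background discusses in degrees. A percentage change in length is not a percentage change in tilt.
- **That distance cuts dose by about two thirds.** That follows at fixed mAs (66-71% under the same geometry), which is not the stated plan, since settings come from phase two.
- **That no habitus-by-distance phantom grid is planned.** The example acquisition procedure is in Figure 2, which was not available for this review.

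**Conclusion.** The point holds for dose and image quality. In phase three posture and SID are perfectly collinear by design, and this conclusion needs no assumption. The contrast as delivered estimates the difference between two technique packages and cannot be attributed to posture. A SAP, which was not available here, could not recover the separation from the phase-three contrast alone. It could only add a model.

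The size does rest on assumptions: an entrance-dose reduction of about 17-28% from distance alone at equal detector exposure with the stated thickness and gap, and less for deeper tissue. That is enough for a modest real penalty from standing to appear as no increase. The documents do not show that such a penalty exists.

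**What to change.** 1. **Reword the aim and research question 1** as a comparison of erect at 180 cm with current supine at 115 cm, or otherwise reconcile the aim with the fixed distances. Question 2 on image quality needs the same reading. State whether phase-two settings apply to both postures.
2. **Add source-object distance to Appendix 7** for both images, since the dose calculation depends on it. Report dose as delivered and standardised to a common SID, with the assumptions stated. For example, if D is the measured source-object distance on the erect image, the skin would lie at D − 65 for an SID of 115 cm. Entrance dose at equal detector exposure is then multiplied by [(115/(D − 65)) / (180/D)]². At D = 149 this is [(115/84) / (180/149)]² = 1.28. For effective dose, rerun the Monte Carlo calculation at the common distance. This is an analysis convention only.
3. **Use the phase-two phantom exposures** at different distances to report the distance and habitus components of dose separately.
4. **If linear measurements are reported**, correct them for magnification.

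The cost is a narrower headline claim, one extra data field and one model-based analysis. Image-quality scores have no such simple correction and should stay a comparison of techniques. No patient exposure is added, and no clinical distance or exposure setting is proposed.

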Descriptive analysis of the participant demographics and the image acquisition parameters will be undertaken, including patient preference and thematic analysis of any free text comments from the radiographer or patient. Comparison of examination length will be undertaken utilising the 'start time' and the time on the last image in that orientation, it is acknowledged this outcome will be influenced by the need for repeat exposures and technical difficulties in this small cohort.

Initial image quality will be assessed in relation to the diagnostic value of the radiograph and whether a repeat x-ray would have been warranted, this will allow comparison of repeat rates for the 2 examinations as well as the reasons. Further assessment of image quality will use a previously validated psychometric scale³¹ to compare the noise at different anatomical regions. This will provide a comparison between the 2 projections, the images will be randomly allocated for analysis and reviewers will be blinded to the acquisition technique (erect or supine) for this analysis to reduce bias and maintain objectivity.

Ethical Consideration

The key ethical issue associated with this research is the requirement for an additional x-ray in phase three. Other options have been explored including using only an anthropomorphic phantom and randomization of patients to either examination. These strategies do not provide sufficient robustness to demonstrate changes on an individual basis and the phantoms have fixed bony and soft tissue anatomy and therefore do not allow comparison of changes related to posture.

REC and HRA approval will be sought to ensure the additional radiation dose is managed within an appropriate framework. This will include establishing protocols to limit radiation exposure through exclusion from the study if repeat x-rays are required due to quality reasons. A patient will only have one radiograph taken in the erect position, regardless of final image appearances. This will ensure that the maximum additional dose for a single patient is limited to one exposure whilst maintaining the integrity of their clinical examination. This will also provide information regarding the potential repeat rate for erect radiographs in a prospective future trial. The study team will then decide whether the patient is excluded from the study, included for limited analysis or fully included despite imaging appearances, on a case by case basis.

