Appendix 7. Phase 3: Data collection sheet

A study to compare supine and erect pelvis radiographs – assessment of impact on radiation dose and diagnostic markers (SEPRAIDD)

Study ID Number:			Imaging order
Patient Hospital Number:			
Height:	m _	Weight:	kg
Age:		Gender:	M / F
Supine radiograph Start time:	Repe	at Yes/No	
kV	kV _		
mAs	mAs		
DAP	DAP		
EI Image time:	EI		
Erect radiograph Start time:	Сог	nments:	
kV			
mAs			
DAP			
EI Image time:			
Patient preference			
Supine / Erect			

Radiographer code:

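### The supine-or-erect preference item cannot show whether erect imaging is acceptable, and random order does not stop preference depending on order

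*Protocol*

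**What the plan says.** Acceptability to patients is the third of the protocol's four key research questions: "Are erect pelvic radiographs acceptable to patients in their performance".

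Under Phase Three, Study procedures, each patient is imaged in both positions: "The supine and erect radiographic examinations will be performed in a random order". The order is pre-printed on the data collection sheets, and the protocol adds: "This will be established using a random number generator". It then states: "This procedure ensures that the patient preference cannot be related to the examination order".

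Under Data collection and management, the patient is asked which of the two techniques they prefer. The sheet in Appendix 7 gives two answers, supine or erect. It has a comments space beside the erect radiograph and a field headed "Imaging order". It has no option for no preference and no item on acceptability or comfort.

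Under Data analysis for phase three, the descriptive analysis is described as "including patient preference and thematic analysis of any free text comments from the radiographer or patient". The protocol does not mention a breakdown of preference by order.

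**The concern.** There are two separate problems, of unequal weight.

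The main one is measurement. Question 3 is absolute: is the erect examination acceptable? The item on the sheet is relative: which of the two does the patient like better? The second does not determine the first. What the sheet does not collect cannot be recovered by any later analysis plan. The first study objective is to develop procedures for a future study, so an unsuitable sheet could be carried into it.

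The lesser one is the sentence about order. It presents an order effect as impossible, which gives a false reason for not looking at preference by order. Randomising order makes order independent of patient characteristics. It does not stop a patient's answer depending on which examination came last.

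**Working it through.** The protocol states no figure for preference or acceptability, so there is nothing to reproduce. The first step is logical. The later steps gauge size under stated assumptions.

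**1. Does preference identify acceptability?** Let E be the share choosing erect, a the share of those patients who find erect acceptable, and b the share of supine-choosers who find erect acceptable. Then

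acceptability = E × a + (1 − E) × b.

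The sheet gives E only. Neither a nor b is collected. Illustration with E = 0.30 (assumed):

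- a = 1, b = 1: 0.30 + 0.70 = 100%
- a = 1, b = 0: 0.30 + 0 = 30%
- a = 0, b = 0: 0%

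The same preference result fits any acceptability from 0% to 100%. In addition, E itself contains indifferent patients who had to choose.

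**2. Can preference depend on order when order is random?** Suppose the chance of choosing erect is 0.5 + d when erect comes second and 0.5 − d when it comes first. With d = 0.20 (assumed) these are 70% and 30%. At a perfect 30:30 split the overall figure is (30 × 0.70 + 30 × 0.30)/60 = 50%, which is undistorted. Preference is nevertheless strongly related to order, so the sentence fails even under ideal balance.

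**3. How uneven could the split be?** Inputs: the phase three minimum of 60 patients (Sample size) and, as an assumption, simple 1:1 randomisation. From the Binomial(60, 0.5) distribution:

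- exactly 30:30: probability 0.10
- 36:24 or worse in either direction: probability 0.155
- central 95% range: 22:38 to 38:22

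**4. How far would an uneven split move the preference percentage?** With f the share imaged erect second, the shift is d × (2f − 1).

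| Assumed share choosing the second examination | d | Shift at 36:24 (2f − 1 = 0.20) |
|---|---|---|
| 55% | 0.05 | 1 point |
| 60% | 0.10 | 2 points |
| 70% | 0.20 | 4 points |
| 80% | 0.30 | 6 points |

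Direct check of the last two rows: (36 × 0.7 + 24 × 0.3)/60 = 0.54 and (36 × 0.8 + 24 × 0.2)/60 = 0.56. At 38:22, 2f − 1 = 16/60, and d = 0.20 gives 5.3 points.

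**5. Comparison with sampling error.** The 95% half-width for a preference of 50% with 60 patients is 1.96 × √(0.25/60) = 0.127, or about 13 points. Each shift in step 4 is well inside that.

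**6. What would a breakdown by order show?** With 30 patients per order, power to detect a difference between orders is 12%, 34%, 65% and 89% for d = 0.05, 0.10, 0.15 and 0.20. Such a table is descriptive. Failing to find a difference would not show that there is none.

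**The case against.** The strongest reply is that the sentence is a clumsy statement of an ordinary and sound reason for randomising. With equal odds, an order effect cancels in expectation, and chance imbalance adds variance but no systematic bias. That stands as a defence of the design, but not of the wording, which rules out any relation at all.

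A reader might infer that the protocol uses unblocked randomisation and ignores order in the analysis. It says neither. A random number generator can also produce a blocked list, and pre-printed sheets are compatible with one. The sheet records imaging order, so preference can be tabulated by order without new data. Whether it will be is a detail that a statistical analysis plan commonly settles.

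A reader might also infer that the share choosing erect is a floor for acceptability. It is not, because a patient may choose erect and find neither position acceptable. Nor do the documents support carrying an order effect over to the examination-time comparison: that would be a different mechanism, and nothing indicates its presence or size.

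On acceptability, it is fair to say that question 3 is not left wholly without evidence. Comments from patient or radiographer are to be analysed thematically, and refusal rates are collected. But comments are optional and give no proportion with a known denominator. Refusal concerns joining a study with an additional x-ray, which is not the same as finding the erect position acceptable. The patient screening questionnaires mentioned under Ethical Consideration are not described as measuring acceptability. It is also true that acceptability is a research question and is not among the listed study objectives. That limits the weight of the point without removing it.

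**Conclusion.** Both parts hold in limited form. The forced supine-or-erect choice cannot give the proportion of patients who find erect imaging acceptable, so question 3 has no direct structured measure. This rests on logic and on the contents of Appendix 7, with no numerical assumption. The sentence claiming that random order excludes a relation between preference and order is incorrect.

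The numerical consequence of the second part is small: about 4 to 6 points at a 36:24 split, against a half-width of about 13 points. That figure assumes simple randomisation, 60 patients, and 70% to 80% choosing whichever examination came second, none of which except the 60 is in the protocol. It does not support a claim that the preference result would be seriously distorted. The point is worth acting on because the missing item is cheap to add now and cannot be recovered afterwards.

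**What to change.** 1. In Appendix 7, add a no-preference option, and add a short acceptability item for each position, for example: *Was the erect x-ray acceptable? Yes/No*, with the same for supine.
2. Report the proportion finding erect acceptable, with its confidence interval, as the answer to question 3. Keep preference as a secondary description.
3. In Phase Three, Study procedures, replace the sentence on order with a statement that order is balanced by randomisation and that preference will be tabulated by the imaging order already recorded.
4. Optionally, generate the order list in blocks so that the two orders stay close to equal in number. This costs nothing.

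The cost is a reprinted sheet, a few more tick-boxes for each patient, and slightly fewer patients expressing a preference. Exposure and imaging procedure are unchanged.
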